6.4. On-Treatment assessments

After randomization, participants will be seen in follow up at 4-week intervals for the first 12 weeks and then at 12 week intervals until therapy is completed, as shown in the Time and Event Chart (Appendix 3). For participants having side effects related to treatment or adherence issues, more frequent visits can be undertaken at the discretion of the study physician. These visits will be conducted as an “Unscheduled Visit” and tests/procedures performed will be at the discretion of the study physician (with the exception of adverse events to be managed per guidelines specified in the protocol or manual of operations, i.e. hepatitis flare or hypophosphatemia).

1. Each outpatient visit will include assessment of compliance, adverse events reporting, vital signs, weight, symptoms evaluation, record of concomitant medications, drug dispensing, and blood testing as detailed in the Time and Event Chart (Appendix 3).
2. Symptom questionnaire at each visit.
3. Depression assessments at weeks 12, 24, 36, 48, and 96.
4. Fatigue questionnaire at weeks 24 and 96.
5. Health Behavior and quality of life questionnaires at weeks 48, 96, and 144.

6. Blood will be drawn for CBC with differential at each visit until week 36 and then CBC without differential at week 48, 96, and 144.
7. Hepatic panel (AST, ALT, total bilirubin) at each visit.
8. A renal panel (creatinine, calculated creatinine clearance, phosphate, blood urea nitrogen, and calcium) at every visit from week 12 on.
9. TSH at weeks 12 and 24.
10. Glucose and triglycerides at week 24.
11. There will be a PT/INR, serum uric acid, and other liver tests (albumin, total protein, alkaline phosphatase, direct bilirubin) at weeks 48, 96, and 144.
12. There will be a urinalysis done at weeks 48, 96, and 144.
13. A fasting urine creatinine and phosphate will be done at week 96.
14. For females of childbearing age, adherence to contraception will be reviewed and a pregnancy test repeated at each visit during the peginterferon treatment phase.
15. Qualitative HBeAg (in patients who were HBeAg-positive at baseline visit) and HBsAg at weeks 48 and 96. If there is HBeAg or HBsAg loss then anti-HBe or anti-HBs will be tested.
16. Qualitative HBeAg and anti-HBe (regardless of HBeAg status at the baseline visit) at weeks 144 and 180.
17. Qualitative HBsAg at week 180.
18. Quantitative HBsAg and HBeAg will be tested at every visit from week 12 on.
19. HBV DNA will be drawn at every visit.

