6.6 Post Treatment assessments (Appendix 4)

1. Outpatient visits will occur at weeks 196, 200, 204, 208, 212, 216, 228, and 240 for participants in both treatment groups.
2. Laboratory testing (liver panel) plus telephone assessment can replace an outpatient visit at weeks 208 and 212 if ALT at the preceding assessment (week 204 and week 208, respectively) is <300 U/L for men or <200 U/L for women and bilirubin is normal (total bilirubin <1.5 mg/dL or direct bilirubin <0.5 mg/dL)

3. Medical history and physical exam at week 240.
4. Clinical evaluation at weeks 196, 200, 204, 208, 212, 216, and 228.
5. Assessment of adverse events and concomitant medications at each visit.
6. Questionnaires (quality of life, depression assessment, fatigue, and health behaviors) at week 240.
7. Symptom questionnaire at each visit.
8. CBC including platelets, alkaline phosphatase, albumin, total protein, and creatinine at week 240.
9. Renal panel (creatinine, calculated creatinine clearance, phosphate, blood urea nitrogen, and calcium) at each study visit for participants who are on Tenofovir
10. Hepatic panel (ALT, AST, albumin, total protein, alkaline phosphatase, total and direct bilirubin) at each visit.
11. Urinalysis at week 240.
12. PT/INR at weeks 196, 200, 204, 216, and 240.
13. Blood samples for serum/plasma at each outpatient visit.
14. Qualitative HBsAg, HBeAg, and anti-HBe at weeks 216 and 240.
15. Anti-HBs and antiviral drug resistance testing at week 240.
16. HBsAg quantification at weeks 204, 216, 228, and 240.
17. HBeAg quantification at weeks 204, 216, 228, and 240.
18. HBV DNA at each outpatient visit
19. Ultrasound exam (If clinically indicated, per AASLD guidelines, done as standard of care) at week 240.
20. Fibroscan (if available and obtained at, or since, the week 180 visit but not later than the week 192 visit) at week 240.

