6.14. Assessment and management of relapse after stopping therapy

6.14.1. Definition of relapse

Virological relapse: Persistent HBV DNA ≥1000 IU/mL during the follow-up period (on at least two samples at least 12 weeks apart, with one of them being more than 24 weeks after stopping therapy) in HBeAg-positive or HBeAg-negative participants.

Biochemical relapse will be defined as an elevated ALT (>30 U/L for females and >45 U/L for males if normal at end of treatment or an increase of 1.5 X end of treatment level if abnormal at end of treatment) on at least two samples at least 12 weeks apart, with one of them being at least 24 weeks after stopping therapy.

An ALT flare will be defined as an ALT level ≥ 300 U/L for males or ≥ 200 U/L for females.

These definitions will be used for data analyses, see section 6.14.2 for criteria to reinitiate treatment.

Monitoring of participants

- Participants with an increase in total bilirubin to ≥ 3 mg/dL or direct bilirubin to ≥ 1 mg/dL or INR ≥ 1.3 (regardless of ALT and HBV DNA levels) must be reassessed as soon as possible and within 1 week for liver panel, PT/INR, CBC, and creatinine. The laboratory testing should continue every week until INR < 1.3 and either total bilirubin < 3 mg/dL or direct bilirubin < 1 mg/dL.
- Participants with an ALT > 1000 U/L for both males and females (regardless of HBV DNA levels) must be reassessed as soon as possible and within 1 week. Thereafter, weekly monitoring of liver panel, bilirubin (total or direct), PT/INR, HBV DNA should continue until ALT ≤ 1000 U/L.
- Participants with an ALT ≥ 300 U/L for males or ≥ 200 U/L for females (regardless of HBV DNA levels) must be reassessed within 1 week and thereafter, every 2 weeks for liver panel, HBV DNA, bilirubin (total or direct), and PT/INR. The laboratory testing should continue until ALT < 300 U/L for males or < 200 U/L for females.
- Participants with an ALT ≥ 150 U/L for males or ≥ 100 U/L for females (regardless of HBV DNA levels) must be reassessed within 4 weeks and thereafter every 4 (± 1) weeks for liver panel, HBV DNA, bilirubin (total or direct), and PT/INR. The laboratory testing should continue until ALT < 150 U/L for males or < 100 U/L for females.

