6.14.2. Criteria for treatment reinitiation in the Post-Treatment Follow up Period

Tenofovir DF will be restarted for any one of the following:

- Any one of the three criteria: INR ≥ 1.3 , total bilirubin ≥ 3.0 mg/dL or direct bilirubin ≥ 1.0 mg/dL, regardless of HBV DNA or ALT level.
- Any clinical decompensation, regardless of HBV DNA or ALT level.
- HBV DNA $\geq 10,000$ IU/mL and ALT > 1000 U/L (male or female) (i.e. only one ALT value > 1000 U/L is needed to qualify).
- HBV DNA $\geq 10,000$ IU/mL and ALT ≥ 300 U/L for males, ≥ 200 U/L for females. A total of one HBV DNA $\geq 10,000$ IU/mL and any three ALT values ≥ 300 U/L (male) or ≥ 200 U/L (female) over the 4-week (or longer) time frame are needed to qualify. Treatment will be resumed if the third ALT remains ≥ 300 U/L (male) or ≥ 200 U/L (female).
- HBV DNA $\geq 10,000$ IU/mL and ALT ≥ 150 U/L for males or ≥ 100 U/L for females. A total of one HBV DNA $\geq 10,000$ IU/mL and any three ALT values ≥ 150 U/L (male) or ≥ 100 U/L (female) over the 12 week (or longer) time period are needed to qualify. Treatment will be resumed if the third ALT remains ≥ 150 U/L (male) or ≥ 100 U/L (female).
- HBsAg-positive and HBeAg-positive at week 192.
- HBsAg-positive, HBeAg-negative, and anti-HBe-negative at week 192

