6.14.3. Management after reinitiation of treatment

Participants who meet criteria for treatment reinitiation specified in section 6.14.2 will be restarted on Tenofovir DF 300mg daily. Tenofovir DF will be provided by the study until week 240. Monitoring of AST, ALT and HBV DNA levels will be done at 4, 8 and 12 weeks after Tenofovir DF is restarted and then every 12 weeks. If bilirubin or INR is abnormal at the time of treatment reinitiation, it (they) should be monitored at 4, 8, and 12 weeks after Tenofovir DF is restarted and then every 12 weeks until it (they) return(s) to normal. If, after treatment reinitiation, the participant meets criteria for non-response (section 6.9) or partial response (section 6.10), the drug therapy will be changed as outlined in those sections.

7. Adverse events and toxicity management

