Appendix 4: Time and event chart after week 192 or treatment discontinuation *

Weeks Post Treatment Discontinuation	4	8	12	16 ⁵	20 ⁵	24	36	48
Study Week	196	200	204	208	212	216	228	240
Medical history								X
Physical exam								X
Clinical evaluation (limited)	X	X	X	X	X	X	X	
Assessment of AE, concomitant meds	X	X	X	X	X	X	X	X
Questionnaires (QOL, Depression assessment, Fatigue questionnaire, and Health behavior)								X
Symptom questionnaire	X	X	X	X	X	X	X	X
CBC including platelets								X
Hepatic panel (AST, ALT, total bilirubin, direct bilirubin)	X	X	X	X	X	X	X	X
Other liver tests (ALKP, total protein, and albumin)	X	X	X	X	X	X	X	X
Renal Panel (Creatinine, calculated CrCl, BUN, Ca, PO₄)**	X	X	X	X	X	X	X	X
Urinalysis								X
PT/INR	X	X	X			X		X
Serum/plasma banking¹	X	X	X			X	X	X
HBeAg						X		X
Anti-HBe²						X		X
Anti-HBs²								X
HBsAg						X		X
HBsAg quant	X	X	X			X	X	X
HBeAg quant³				X		X	X	X
Quant HBV DNA	X	X	X			X	X	X
Antiviral drug resistance testing								X
Ultrasound exam⁴								X
Fibroscan (if available)								X ⁶

*Schedule is used for participants:

- (i) Those who meet criteria for stopping treatment at week 192 regardless of whether they stop treatment
- (ii) Those who stopped treatment early due to meeting criteria for treatment failure (non-response, partial response, virologic breakthrough);
- (iii) Those stopping treatment early due to an adverse event
- (iv) For those not eligible to stop treatment, visits only occur at study weeks 204, 216, 228, and 240

** Renal panel should be obtained at each study visit for participants who are on treatment. All participants should have creatinine tested at week 240

¹16mL of serum and 8mL of plasma at week 12, 24 and 48, 8mL of serum and 8mL of plasma at other time points

²Anti-HBe/Anti-HBs to be done at next visit if HBeAg/HBsAg becomes negative.

³In participants who are HBeAg positive in qualitative assay

⁴If clinically indicated, per AASLD guidelines, done as standard of care

⁵A hepatic panel and telephone follow-up (minimal assessment) may replace an outpatient visit if ALT at the preceding visit is <300 U/L for males or <200 U/L females and bilirubin is normal (total bilirubin <1.5 mg/dL or direct bilirubin <0.5 mg/dL)

⁶Fibroscan (if available) to be performed at week 240 if obtained at week 180 or 192 visits.

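### Section 6.14.1: weekly bilirubin/INR testing after treatment can end while direct bilirubin is still at the level that starts it

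*Combined protocol and SAP*

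**What the plan says.** The rule is the first bullet under the monitoring heading in section 6.14.1.

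- **Start.** The bullet opens "Participants with an increase in total bilirubin to" and lists three alternatives: total bilirubin ≥3 mg/dL, direct bilirubin ≥1 mg/dL, or INR ≥1.3, whatever the ALT and HBV DNA. Any one of them requires reassessment within a week.
- **Stop.** "The laboratory testing should continue every week until INR" is below 1.3 and, in addition, either total bilirubin is below 3 mg/dL or direct bilirubin is below 1 mg/dL.

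Four other places bear on it.

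- **Section 6.14.2** restarts tenofovir DF at the same three limits, introduced by "Any one of the three criteria: INR". Direct bilirubin of 1.0 mg/dL is enough alone.
- **Section 6.14.3** covers bilirubin or INR that is abnormal at restart: "it (they) should be monitored at 4, 8, and 12 weeks after Tenofovir DF is restarted and then every 12 weeks", until normal.
- **The ALT bullets in 6.14.1** each stop at the exact complement of their trigger. The one for ALT above 1000 U/L reads "Thereafter, weekly monitoring of liver panel, bilirubin (total or direct), PT/INR, HBV DNA should continue until ALT" is at or below 1000.
- **The post-treatment hepatic panel** includes both bilirubin fractions: "Hepatic panel (ALT, AST, albumin, total protein, alkaline phosphatase, total and direct bilirubin) at each visit" in section 6.6, and "Hepatic panel (AST, ALT, total bilirubin, direct bilirubin" in Appendix 4.

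**The concern.** A stop rule for safety monitoring should be met only when the condition that started the monitoring has cleared. Here the start rule joins its three limits with *or*, so the stop rule has to join the three opposite conditions with *and*. The bullet does this for INR but keeps *or* between the two bilirubin fractions.

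A participant whose only abnormality is direct bilirubin at or above 1 mg/dL can therefore satisfy the stop clause at the first retest with that value unchanged. This participant has recently been withdrawn from antiviral therapy. Section 7.3.a names close follow-up after stopping as the protocol's answer to the labelled risk of hepatitis exacerbation, and direct bilirubin at this level is the protocol's own signal to resume treatment. At stake is the frequency of testing during a possible deterioration, and whether sites apply the bullet in the same way.

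**Working it through.** There is no published figure to reproduce; the check is one of logic.

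**Inputs (section 6.14.1).** Write T for total bilirubin ≥3 mg/dL, D for direct bilirubin ≥1 mg/dL and I for INR ≥1.3.

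- Start = T or D or I
- Stop as written = not I, and (not T or not D)
- Stop as the complement of start = not I and not T and not D

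**Enumeration.** Three yes/no conditions give 2³ = 8 combinations. One has no abnormality, so 8 − 1 = 7 meet the trigger.

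| T | D | I | Start met | Stop as written | Stop as complement |
|---|---|---|---|---|---|
| no | no | yes | yes | no | no |
| no | yes | no | yes | **yes** | no |
| no | yes | yes | yes | no | no |
| yes | no | no | yes | **yes** | no |
| yes | no | yes | yes | no | no |
| yes | yes | no | yes | no | no |
| yes | yes | yes | yes | no | no |
| no | no | no | no | yes | yes |

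Start and stop hold together in 2 of 7 trigger patterns as written, and in 0 of 7 with the complement.

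**The two overlapping patterns.**

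1. *Direct only.* Take illustrative values of total 2.5, direct 1.5 and INR 1.1. Direct 1.5 ≥ 1, so start holds. INR 1.1 < 1.3 and total 2.5 < 3, so stop also holds. Direct 1.5 ≥ 1.0, so the 6.14.2 restart criterion holds too.
2. *Total only.* Total is at least 3 with direct below 1 and INR below 1.3. This may be benign unconjugated elevation; section 4.1, item 7, allows for Gilbert's syndrome at entry. The point does not rest on this pattern.

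**Comparison with neighbouring rules.** The three ALT bullets pair >1000 with ≤1000, ≥300/200 with <300/200, and ≥150/100 with <150/100 (males/females), all exact complements. Section 6.12 lets a participant with an on-treatment flare continue only if total is below 2.0 *and* direct is below 1.0, so both fractions must be acceptable there.

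**What remains after release from weekly testing.** The 6.14.1 trigger and the first 6.14.2 restart criterion share their limits, so everyone who triggers weekly testing should also restart tenofovir DF. For them 6.14.3 requires checks at 4, 8 and 12 weeks, then every 12 weeks until normal. For anyone who does not restart, 6.14.3 does not apply and Appendix 4 governs: after week 216 its visits fall at weeks 228 and 240, with no PT/INR at week 228.

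**The case against.** **An innocent reading exists.** The *or* may mean that whichever fraction was measured can show resolution. The ALT bullets refer to bilirubin as either fraction. Section 6.6 (item 2), section 6.13.3 and Appendix 4 (footnote 5) define normal bilirubin as total below 1.5 or direct below 0.5 mg/dL. The on-treatment panel in section 6.4 lists total only: "Hepatic panel (AST, ALT, total bilirubin) at each visit". This may well explain how the wording arose. It does not make release at direct ≥1 mg/dL a sensible rule when both fractions are on the post-treatment panel, and the bullet does not limit itself to a missing fraction.

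**The start clause may apply again.** A retest with direct bilirubin still at 1 or more could be read as invoking the one-week reassessment afresh. That is possible, but then the bullet tells the site both to stop and to continue.

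**Restart may make the point moot.** This is the strongest objection. If the 6.14.3 schedule replaces weekly testing once tenofovir DF is resumed, the stop clause matters only before restart, or in someone who does not restart. The documents do not say which schedule governs. Because the trigger and restart limits are identical, the weekly instruction has real work to do mainly if it runs alongside restart, but that is an inference. A reader might conclude that the protocol already requires weekly testing after restart; it does not say so.

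**Other backstops.** Section 6.13.3 allows extra safety visits, section 7.6.2 follows unresolved adverse events, and the ALT bullets separately require bilirubin and INR when ALT is at least 150 U/L (males) or 100 U/L (females). These stand. They limit the consequence without repairing the stop rule.

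**Conclusion.** The stop clause is not the complement of the start clause. The case that matters is direct bilirubin ≥1 mg/dL with total <3 mg/dL and INR <1.3, which meets start, stop and the restart criterion together. That follows from the text and needs no assumption beyond reading *either … or* literally.

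The effect is small and confined to the frequency of safety monitoring. Three stronger readings might be inferred and are not supported:

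- *Follow-up or treatment is lost.* It is not. Restart is required under 6.14.2, later checks under 6.14.3 continue until values are normal, and adverse-event follow-up applies.
- *The pattern counts describe participants.* They count rows of a logic table. The documents give no frequency for any pattern, so neither the number affected nor the number of tests lost can be estimated.
- *The trial's results are at risk.* No endpoint, analysis or sample-size figure depends on this rule.

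It is worth correcting because it is a stated safety rule that contradicts itself, and the correction is cheap.

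**What to change.** In section 6.14.1, change the stop clause so that weekly testing continues until INR is below 1.3 **and** total bilirubin is below 3 mg/dL **and** direct bilirubin is below 1 mg/dL. State that both fractions are measured at each weekly retest, so that a missing fraction cannot end testing; both are already on the post-treatment panel.

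Two additions are tempting but should be left out. An exception for Gilbert's syndrome in the stop clause alone would recreate the mismatch, because total ≥3 mg/dL would still meet the start and restart rules. Requiring weekly testing after restart would be a new obligation on top of 6.14.3. At most, ask the sponsor to state which schedule governs after restart.

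The cost is one changed sentence and a few extra blood draws in affected participants. Suppose restart occurs at the trigger and direct bilirubin stays at or above 1 mg/dL for four weeks. If weekly testing runs alongside 6.14.3, draws fall at weeks 1, 2, 3 and 4. The week 1 retest (6.14.1) and week 4 check (6.14.3) are already required, so 4 − 2 = 2 are added, fewer if a scheduled visit falls there. If 6.14.3 replaces weekly testing from restart, none is added.

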6.14.2. Criteria for treatment reinitiation in the Post-Treatment Follow up Period

Tenofovir DF will be restarted for any one of the following:

- Any one of the three criteria: INR ≥ 1.3 , total bilirubin ≥ 3.0 mg/dL or direct bilirubin ≥ 1.0 mg/dL, regardless of HBV DNA or ALT level.
- Any clinical decompensation, regardless of HBV DNA or ALT level.
- HBV DNA $\geq 10,000$ IU/mL and ALT > 1000 U/L (male or female) (i.e. only one ALT value > 1000 U/L is needed to qualify).
- HBV DNA $\geq 10,000$ IU/mL and ALT ≥ 300 U/L for males, ≥ 200 U/L for females. A total of one HBV DNA $\geq 10,000$ IU/mL and any three ALT values ≥ 300 U/L (male) or ≥ 200 U/L (female) over the 4-week (or longer) time frame are needed to qualify. Treatment will be resumed if the third ALT remains ≥ 300 U/L (male) or ≥ 200 U/L (female).
- HBV DNA $\geq 10,000$ IU/mL and ALT ≥ 150 U/L for males or ≥ 100 U/L for females. A total of one HBV DNA $\geq 10,000$ IU/mL and any three ALT values ≥ 150 U/L (male) or ≥ 100 U/L (female) over the 12 week (or longer) time period are needed to qualify. Treatment will be resumed if the third ALT remains ≥ 150 U/L (male) or ≥ 100 U/L (female).
- HBsAg-positive and HBeAg-positive at week 192.
- HBsAg-positive, HBeAg-negative, and anti-HBe-negative at week 192

6.14.3. Management after reinitiation of treatment

Participants who meet criteria for treatment reinitiation specified in section 6.14.2 will be restarted on Tenofovir DF 300mg daily. Tenofovir DF will be provided by the study until week 240. Monitoring of AST, ALT and HBV DNA levels will be done at 4, 8 and 12 weeks after Tenofovir DF is restarted and then every 12 weeks. If bilirubin or INR is abnormal at the time of treatment reinitiation, it (they) should be monitored at 4, 8, and 12 weeks after Tenofovir DF is restarted and then every 12 weeks until it (they) return(s) to normal. If, after treatment reinitiation, the participant meets criteria for non-response (section 6.9) or partial response (section 6.10), the drug therapy will be changed as outlined in those sections.

7. Adverse events and toxicity management

7.1. Criteria for permanent and premature discontinuation of treatment

- Death
- Grade IV toxicity (laboratory or clinical)
- Hepatic decompensation defined by:
 - Total bilirubin ≥ 2.0 mg/dL and direct bilirubin ≥ 1.0 mg/dL
 - Any clinical decompensation

7.2.a. Adverse effects of peginterferon alfa-2a

Common side effects of peginterferon alfa-2a include influenza-like symptoms, particularly with the first few injections, fatigue, neuropsychiatric symptoms such as depression and reduction in white blood cell counts and platelet counts. Hyper- or hypothyroidism has been noted to occur in up to 5% of participants receiving peginterferon alfa-2a.

Some rare but potentially serious side effects include:

- neuropsychiatric complications, which may include suicide, suicidal ideation, acute psychosis and severe depression
- serious and severe bacterial infections; fatal infections have been reported during treatment with peginterferon alfa-2a
- pancreatitis
- interstitial pneumonitis, fatal cases have been reported with peginterferon alfa 2a use

Other possible but uncommon adverse events associated with peginterferon alfa-2a include:

- development or exacerbation of existing autoimmune disorders such as rheumatoid arthritis, systemic lupus erythematosus, idiopathic thrombocytopenic purpura, hemolytic anemia, type 1 diabetes, psoriasis, etc.
- pulmonary disorders including dyspnea, pulmonary infiltrates, and sarcoidosis
- exacerbations of inflammatory bowel disease
- eye disorders, including decrease or loss of vision, retinal hemorrhages
- hearing disorders, including loss of hearing and tinnitus
- hypersensitivity reactions including severe skin reactions, in the spectrum of Stevens Johnson syndrome

7.2.b. Peginterferon alfa-2a dose reductions

Factors that will lead to a reduction in the dose of peginterferon alfa-2a include:

1. Disabling symptoms, which, in the opinion of the study physician, are related to peginterferon alfa-2a treatment and prevent the participant from performing his/her occupation or daily tasks.
2. A rash consistent with allergic reaction or vasculitis.
3. Reductions in the neutrophil count according to the guidelines in Appendix 2.
4. A reduction in platelet count according to the guidelines in Appendix 2.
5. Any adverse reaction, which, in the opinion of the study physician, places the participant at increased risk of a serious adverse effect.

The dose of study medications may be decreased due to adverse events or laboratory abnormalities. The weekly dose of peginterferon alfa-2a will be reduced in graduated steps as follows:

- Level 1 decrease from 180 µg to 135 µg
- Level 2 decrease from 135 µg to 90 µg
- Level 3 decrease from 90 µg to 45µg

For participants who require a downward dose adjustment for neutropenia or thrombocytopenia, laboratory values should be repeated, if practical, prior to the next dose of peginterferon alfa-2a to confirm the result and dictate the course of action. Participants who remain with a neutrophil count below 500/mm³ (but above 250/mm³) or a platelet count below 50,000/mm³ (but above 25,000/mm³) should receive stepwise dose reductions until levels of neutrophils and platelets are $\geq 500/\text{mm}^3$ or 50,000/mm³, respectively, or until a dose of 45 µg of peginterferon alfa-2a is reached. Participants who have a neutrophil count below 250/mm³ or a platelet count below 25,000/mm³ should have their peginterferon alfa-2a dose held. Peginterferon alfa-2a may be resumed at the previous reduced dose when the neutrophil count has been above 500/mm³ or platelet count above 50,000/mm³ on 2 occasions at least 1 week apart.

7.2.c. Guidelines for subsequent peginterferon alfa-2a dose adjustments

Once a participant's dose has been decreased for laboratory abnormalities or adverse events, the study physician may attempt to increase the dose back to or toward the previous stable level only if the following conditions are satisfied:

1. The event or circumstance responsible for the dosage adjustment has resolved or improved;
2. The participant has been at the lower dose for ≤ 4 consecutive doses;
3. The participant had ≤ 6 total doses administered at the lower level during the entirety of the treatment period.

If four or more consecutive doses of peginterferon alfa-2a are held or otherwise not administered (i.e., the participant has not received test medication for more than 28 days), the participant will be considered intolerant of the test medication or non-compliant, whichever is more appropriate to the clinical situation. In such cases, the study physician will discontinue peginterferon alfa-2a but tenofovir DF treatment will continue.

Every attempt will be made to keep those participants randomized to treatment with peginterferon alfa-2a on therapy by dose reduction. The use of hematological growth factors during the study will not be allowed.

7.2.d. Screening and management for depression

The CES-D will be used, along with the study physician's judgment, to screen participants for depression at the screening visit (8 weeks prior to randomization) and to monitor for onset or worsening of symptoms during the treatment.

Screening Visit (8 weeks prior to randomization): If the participant has a CES-D score >15 at the screening visit (8 weeks prior to randomization), clearance from a mental health provider may be considered at the discretion of the study physician. In addition to clarifying possible psychiatric disorders, the mental health provider may advise on the need for adjuvant medical or counseling therapy and suitability for enrollment.

During treatment: Potential mood disturbance/medication intolerance will be assessed at each visit by study personnel. The CES-D will be administered every 12 weeks for 48 weeks. If the participant has a score >15, the study physician will determine whether referral to a mental health provider is indicated. If the participant has a score of at least 27, the study physician will refer to a mental health provider for evaluation and management. Any participant who develops recurrent suicidal ideation, a suicide plan and/ or makes a suicide attempt should have peginterferon alfa-2a immediately discontinued and be referred to a mental health provider for further management.

Suggested guidelines for peginterferon alfa-2a dose reduction:

- Unpleasant and/or disabling side effects might prompt dose reduction, but this is not required.
- A CES-D score of 16-26 might prompt further consideration of dose reduction, but is not a requirement for dose reduction.
- A score of at least 27 should prompt attention from the PI and dose reduction or discontinuation be considered.

If the management of the depression is not successful after eight weeks or if the participant develops suicidal or homicidal ideation, the peginterferon alfa-2a will be stopped but tenofovir DF continued until the end of the treatment period. The participant will be referred to a mental health provider.

7.3.a. Adverse effects of tenofovir DF

All nucleoside and nucleotide analogues carry a warning about the risk of lactic acidosis and severe hepatomegaly and steatosis because of the possibility of mitochondrial injury.

Tenofovir DF has been associated with instances of lactic acidosis, but only in participants receiving other medications that have been associated with this complication, such as didanosine, stavudine and zidovudine. It is not clear whether tenofovir DF when used by itself or in combination with peginterferon alfa-2a, is associated with mitochondrial toxicity either to the liver (lactic acidosis, acute fatty liver and hepatic failure), muscle (myositis), nerves (neuropathy) or pancreas (acute pancreatitis).

In addition, all agents with activity against HBV replication carry a warning label about the risk of exacerbation of hepatitis after discontinuation of treatment. This issue is addressed by the protocol design and close follow-up of participants after stopping therapy (see section 6.6, 6.14.1, and Appendix 4).

7.3.b. Tenofovir DF and renal function

Tenofovir DF is principally eliminated by the kidney. Renal impairment, including cases of acute renal failure and a Fanconi-like syndrome (proximal renal tubular dysfunction with severe hypophosphatemia), has been reported.

Adverse Event Monitoring and Management Related to Elevated Serum Creatinine (Cr)
Nephrotoxicity will be based upon serum creatinine results:

- If Cr \geq 0.5 mg/dL above baseline, repeat testing within 72 hrs will be performed and drug continued unless the study physician considers drug discontinuation necessary.
- If Cr increases to \geq 1.2 mg/dL and by \geq 0.3 mg/dL from baseline, additional testing at the next scheduled visit should be considered (see Manual of Operations). If Cr \geq 1.2 mg/dL and $>$ 0.5 mg/dL above baseline on two consecutive occasions, the study drugs will be discontinued and not restarted unless another, reversible cause of creatinine elevations is identified. If the study physician identifies an alternative cause for the increase in Cr, study drugs may be resumed at discretion of study physician if calculated Cr clearance is $>$ 30 ml/min with tenofovir DF dose adjustment.
- Any study participant discontinued from the study will be recommended to commence anti-HBV therapy with an alternative HBV drug immediately (this drug will not be provided by the study).

Tenofovir DF Dosing is Based Upon Creatinine Clearance (CrCL)

Creatinine clearance will be calculated in all participants prior to initiating therapy and at each study visit to determine tenofovir DF dose.

- Participants whose calculated creatinine clearance decreases to $<$ 50 ml/min should have this value confirmed within 72 hrs. If confirmed to be 30-50 ml/min, the dosing frequency for tenofovir DF should be adjusted from every 24 hours to every 48 hours until the calculated creatinine clearance returns to $>$ 50 ml/min.
- Participants whose calculated creatinine clearance decreases to $<$ 30 ml/min, will be permanently discontinued from treatment and enter the follow-up phase.

Adverse Event Monitoring and Management of Hypophosphatemia:

If serum phosphate falls below 2.5 mg/dL and by at least 0.5 mg/dL from baseline, consider phosphate supplementation. Additional testing at the next scheduled visit should be considered (see Manual of Operations).

- If the serum phosphate is $<$ 1.4 mg/dL, repeat testing within one week will be performed and supplementation provided as per manual of operations. If serum phosphate is $<$ 1.4 mg/dL on repeat testing, urine and serum phosphate and creatinine will be determined to assess maximal phosphate tubular reabsorption and blood test should be performed to check potassium, calcium, bicarbonate, BUN and Cr.
- Tenofovir DF dosing may be interrupted and aggressive supplementation with intravenous (if symptomatic) or oral (if no symptoms) phosphorus should be used. Repeat phosphate testing weekly until corrected to lower limit of normal range. If this intervention does not correct phosphate level in 2 weeks, Tenofovir DF should be permanently discontinued.
- If serum phosphate is $<$ 1.0 mg/dL, participant will be asked to return immediately for further evaluation and treatment and Tenofovir DF dosing will be discontinued.

Any study participant discontinued from the study will be recommended to commence anti-HBV therapy with an alternative HBV drug immediately (this drug will not be provided by the study).

7.3.c. Tenofovir DF and bone mineral density

Decreases in bone mineral density have been observed in participants taking tenofovir DF for prolonged periods in the context of treatment for HIV infection. These changes have been associated with significant increases in biochemical markers of bone metabolism, suggesting increased bone turnover. Although the pathogenesis of these changes are not certain, they may be related to proximal renal tubulopathy, phosphate loss and a form of secondary hyperparathyroidism.

Serum calcium, phosphate and creatinine levels will be monitored. Serum vitamin D levels will be measured at baseline and supplements prescribed for the participants as clinically indicated. Participants will have bone densitometry done prior to initiating therapy if clinically indicated (as standard of care). If either osteopenia or osteoporosis is present on the bone densitometry done prior to initiation of treatment, the participant can be enrolled as long as he/she is concurrently treated for osteopenia or osteoporosis. Repeat bone densitometry may be performed if clinically indicated (as standard of care).

7.3.d. Discontinuation of tenofovir DF for selected biochemical abnormalities

Tenofovir DF will be permanently discontinued and the participant considered a treatment failure for Grade 3 hypophosphatemia (1.0-1.4 mg/dL) that does not correct within 2 weeks with phosphate supplements or Grade 4 hypophosphatemia (<1.0 mg/dL) or otherwise unexplained serum creatinine elevations by ≥ 1.2 mg/dL and ≥ 0.5 mg/dL above baseline on two consecutive occasions or calculated creatinine clearance <30 ml/min that develop on therapy. For lesser degrees of renal insufficiency not requiring discontinuation, the dose of tenofovir DF will be adjusted according to the manufacturer's recommendation.

